## 18 Other Contents Required Description

The details of Finance and Insurance and Publication Policy, please see the contracts with sites.

**Appendix 1 Qualification Documents (supplied alone)**

Relevant qualification documents of sponsor.

This statistical analysis plan (SAP) is based on Protocol KCI.VERAFLO.2018.02., dated 06 September, 2019 (include amended protocol dated 23AUG2022 V2.0).

2. Changes to Planned Analyses as Stated in Protocol

Not applicable.

3. Study Objectives

3.1. PRIMARY OBJECTIVE

To demonstrate non-inferiority in the wound volume reduction rate of investigational group versus control group patients with open wounds that have extensive soft tissue damage.

3.2. SECONDARY OBJECTIVES:

To compare the differences of time to completion of wound bed preparation, wound area reduction rate, wound clinical assessments, incidence of adverse events (AEs) / serious adverse events (SAEs) and device deficiencies in investigational group versus control group.

4. Study Design

4.1. GENERAL DESCRIPTION

This is a prospective, multicenter, randomized (1:1), open-label, parallel controlled, non-inferiority trial evaluating the efficacy and safety of V.A.C. VERAFL™ Dressing Kit versus Negative Pressure Wound Drainage Material (Guangdong Shuangling Pharmaceuticals Co., Ltd.) for wound bed preparation in open wounds with extensive soft tissue damage. This is a pre-marketing trial of V.A.C. VERAFL™ Dressing Kit in China for National Medical Products Administration (NMPA) registration. It is anticipated that the primary efficacy endpoint (wound volume reduction rate) of investigational group is non-inferior to that of control group. Approximately 140 subjects who meet the eligibility criteria will be randomized to the investigational group or control group at the ratio 1:1.

Debridement is not permitted during study treatment. Therefore, subjects will only be enrolled following definitive surgical debridement (if serial debridements performed) of the target wound. The target wound for each subject in both groups will be treated for up to 14 days or until deemed ready for closure by the investigator (whichever occurs first). Following study treatment, the wound may be treated with any standard therapy selected by the physician, and then accepted secondary intervention for wound closure according to the wound bed preparation situation. The planned study

period consists of the following visits: Screening (Day -3 to 0), Day of randomization (Day0), Dressing change visit(s), End of treatment visit. The following data in both groups will be recorded and collected: wound volume reduction rate, time to completion of wound bed preparation, wound area reduction rate, incidence of AEs / SAEs and device deficiencies. The efficacy and safety of V.A.C. VERAFL™ Dressing Kit in treating open wounds that have extensive soft tissue damage will be evaluated according to the above data.

4.2. SCHEDULE OF ACTIVITIES

Schedule of events can be found in Section 7.2.2 of the protocol.

5. Planned Analyses

The following analyses will be performed for this study:

- Sample Size Re-estimation
- Final Analysis

5.1. DATA MONITORING COMMITTEE (DMC)

There will be no DMC for this study.

5.2. SAMPLE SIZE RE-ESTIMATION

There will be no unblinded interim analysis for this study. A blinded check of the sample size assumptions will take place once at least 70 evaluable subjects have been enrolled.

5.3. FINAL ANALYSIS

All final, planned analyses identified in this SAP will be performed by Kun Tuo Biostatistics following Sponsor Authorization of this Statistical Analysis Plan and Database Lock.

5.4. SAMPLE SIZE CALCULATION

The number of evaluable subjects required for this trial is 128 subjects (64 per treatment arm). To account for a potential 10% drop-out rate, at least 140 subjects (70 per treatment arm) will be randomly assigned in a 1:1 allocation ratio to V.A.C. VERAFL™ or control group.

140 evaluable subjects (70 per study arm) will achieve approximately 80% power to detect a difference with a non-inferiority margin of 20% based on a one-sided t test with a significance level of 0.025 and pooled standard deviation being 40%.

Due to the uncertainty in the actual variability and trying to limit the study size to those strictly needed, a sample size re-estimation will be performed after 50% evaluable subjects per arm (70 subjects total) have completed End of Treatment Visit. This number of subjects is expected to provide a sufficiently precise calculation of the variability in the actual study population.

The point estimate for the pooled standard deviation will be used for the sample size re-estimation. If the re-estimated sample size is greater than 140, the sample size may be increased up to a maximum of 200 subjects to provide sufficient power for this study. If the re-estimated sample size is less than 140, the sample size of the study is still 140.

Considering the actual drop-out rate during the clinical trial, the drop-out rate needs to be adjusted from the expected 10% to 25%. The sample size will increase by 30 subjects, to a total of maximum 170 subjects.

170 evaluable subjects (85 per study arm) will achieve approximately 80% power to detect a difference with a non-inferiority margin of 20% based on a one-sided t test with a significance level of 0.025 and pooled standard deviation being 40%.

6. ANALYSIS SETS

Agreement and authorization of subjects included/ excluded from each analysis set will be conducted prior to database lock. Prior to the blinded check of the sample size assumptions, the agreement and authorization of subjects excluded/included from the primary dataset (that is, identifying the evaluable subjects) will also be conducted.

6.1. PER PROTOCOL SET (PPS)

PPS is the subset of the FAS, including subjects randomized to receive either VAC VERAFL0 or control treatment who do not have major protocol deviations impacting the primary efficacy analysis. It is the primary analysis set for efficacy evaluation.

The rules for exclusion of subjects from the per protocol set (PPS) are as follows:

- Missing baseline volume measure
- Missing end-of-treatment (EOT) volume measure
- Not completing the study (evaluable subjects will have completed the study if deemed ready for closure by investigator or had a treatment duration of up to 14 days*)
- Violating wound size inclusion criterion (maximum depth at baseline < 0.8cm or wound dimensions < 8cm by 1cm) as determined by Independent Assessor (IA)
- Baseline or EOT wound volume measures deemed unreliable after image review (i.e. laser line coverage inadequate, or depth unreliable, or poor margin visibility, or entire wound not imaged, or no comparison across time possible)
- major protocol deviations that would impact the primary endpoint as judged by the medical monitor. For example, post-baseline study wound debridement.

* actual treatment durations of evaluable subjects may be greater than 14 days. Minor protocol deviations should be written for treatment durations outside of the protocol defined window.

There are major PDs defined in the medical monitoring plan (MMD) that do not impact the primary efficacy endpoint. For example, major PDs related to informed consent do not impact the primary efficacy endpoint or interpretation of the primary efficacy analysis.

6.2. FULL ANALYSIS SET (FAS)

Including all subjects who have received either VAC VERAFL0 or control treatment. It is the secondary analysis data set for efficacy evaluation. FAS will be analyzed according to the planned treatment group (as randomized).

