## 6.2 Analysis Data Set

**Full Analysis Set (FAS):** including all subjects randomized to receive either V.A.C. VERAFLTM Dressing Kit or control treatment. It is the secondary analysis set for efficacy evaluation, such as the time to completion of wound bed preparation, rate of wound area reduction, and changes in granulation tissue.

**Per Protocol Set (PPS):** PPS is the subset of the FAS. It is the primary analysis data set for efficacy evaluation.

**Safety Set (SS):** including all subjects who have received either V.A.C. VERAFLTM or control treatment. The data set is used to evaluate the safety of this trial.

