6.3. SAFETY SET (SS)

Including all subjects who have received either VAC VERAFL0 or control treatment. The data set is used to evaluate the safety of this trial. SS will be analyzed according to the actual treatment group.

7. General Considerations

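### SAP 6.2 narrows the full analysis set from all randomised subjects to treated subjects and does not declare the change

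*SAP*

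**What the plan says.** Protocol 6.2 keeps two populations apart. Its FAS is wide, "including all subjects randomized to receive either" the study dressing or control, and its Safety Set is limited to those who were actually treated.

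SAP 6.2 gives the FAS a different membership: "Including all subjects who have received either VAC VERAFL0 or control treatment. It is the secondary analysis data set for efficacy evaluation". SAP 6.3 uses the same membership wording for the Safety Set: "Including all subjects who have received either VAC VERAFL0 or control treatment. The data set is used to evaluate the safety of this trial". The grouping differs. For the FAS, "FAS will be analyzed according to the planned treatment group (as randomized"; for the Safety Set, "SS will be analyzed according to the actual treatment group".

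The SAP says that it rests on the 2019 protocol and notes "include amended protocol dated 23AUG2022 V2.0". Its section headed "Changes to Planned Analyses as Stated in Protocol" is answered as not applicable. Protocol 6.6 requires changes to the analysis methods made before data lock to be recorded in the SAP.

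The per-protocol set (PPS) is the primary efficacy set in both documents (protocol 6.2 and 6.5.1; SAP 6.1 and 15.1.3). The FAS carries the sensitivity analysis of the primary endpoint (SAP 15.1.4), the secondary efficacy endpoints (SAP 15.2) and the exploratory endpoints (SAP 16).

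**The concern.** A subject who is randomised but never receives a study dressing is in the protocol's FAS but in no efficacy set of the SAP. The exclusion happens after randomisation, and nothing in the SAP mentions or justifies it.

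The trial is open-label (protocol 5.1.2.4). In the Day 0 sequence of protocol 5.5.2.2, randomisation comes immediately before the assigned therapy is applied. The subject and the staff can therefore know the arm before the first dressing, and a decision not to start could depend on it. A treated-only set cannot simply be assumed to be balanced.

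Two features make this worth correcting. First, the primary analysis is per protocol, so the FAS is the wider set against which a reader will judge it. Second, time to completion of wound bed preparation is counted from randomisation (protocol 5.3.1.2; SAP 15.2.2), so restricting the set to treated subjects conditions on something that happens after the clock has started.

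**Working it through.** **1. The plan's own sample size.** Inputs from protocol 6.1.1: margin 20 points, SD 40 points, one-sided alpha 0.025, power 80%, true difference taken as 0.

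- Normal approximation: n per arm = 2 × 40² × (1.960 + 0.842)² / 20² = 62.8, so 63.
- Exact t calculation: 64 per arm, power 0.801 (63 per arm gives 0.795). This reproduces the stated 64 per arm, 128 in all.
- Drop-out: 128 / 0.90 = 142.2 (stated 140); 128 / 0.75 = 170.7 (stated 170).

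The calculation is built on evaluable subjects, meaning those in the PPS. The FAS definition does not enter it, so changing that definition leaves the sample size where it is.

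**2. The definitions side by side.**

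| Set | Members | Grouped by |
|---|---|---|
| Protocol FAS (6.2) | all randomised | not stated in 6.2 |
| Protocol Safety Set (6.2) | all treated | not stated in 6.2 |
| SAP FAS (6.2) | all treated | planned arm |
| SAP Safety Set (6.3) | all treated | actual treatment |

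The SAP FAS and Safety Set have identical members. The difference from the protocol FAS is exactly the group randomised but never treated.

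**3. Where that group goes.** It cannot enter the PPS under either document, because the PPS is a subset of the FAS and protocol 6.3 requires the specified treatment to have been received. Under the protocol it would be in the FAS. Under the SAP it is in neither. SAP section 10 also reports deviations among randomised patients within the FAS, a denominator that the SAP's own FAS cannot supply if any randomised subject went untreated.

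**4. How many subjects.** The documents give no number. As an assumption, if 0%, 1%, 2%, 5% or 10% of 170 were never treated, the counts are 0, 1.7, 3.4, 8.5 and 17. Taken as 0, 2, 3, 8 and 17 subjects, these leave a SAP FAS of 170, 168, 167, 162 and 153, against 170 under the protocol.

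**5. What a fix must touch.** SAP 7.1 sets the reference date at the first device application, and SAP 7.2 defines baseline relative to it. Neither exists for an untreated subject. The Day 0 image does exist, because protocol 5.5.2.2 lists imaging before randomisation. SAP 15.2.2 already censors subjects with no post-baseline image at Day 0, and SAP 15.1.2 and 15.2.1 already plan multiple imputation of volume and area in the FAS.

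**The case against.** A reader might infer that the trial has lost its as-randomised analysis, or that the FAS analysis merely repeats the Safety Set. The documents do not support that. SAP 6.2 analyses the FAS by planned arm, so a treated subject who received the other device stays in the randomised arm. What is missing is an analysis of *all* randomised subjects.

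A reader might also link the change to the 25% drop-out rate. That would overstate it. Most routes out of the PPS, such as a missing end-of-treatment volume, non-completion, unreliable images or later debridement, concern treated subjects. They remain in the SAP FAS, with multiple imputation where the volume is missing. Only subjects lost between randomisation and first dressing are affected.

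That gap is probably narrow. Randomisation follows debridement, imaging and a second eligibility check, and treatment is the next listed step on the same day. SAP section 9 also reports the numbers randomised and the numbers in each analysis set by treatment group, so a shortfall should be visible. This stands, and it limits the size of the point. It does not remove it: showing a count is not the same as analysing the subjects.

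One could posit a large effect. For example, if 4 of 85 in one arm were untreated and did 50 points worse, that arm's treated-only mean would be too favourable by 4 × 50 / 85 = 2.4 points against the 20-point margin. Nothing in the documents supports those inputs. Standard multiple imputation would also not recover such a deficit, because it would draw values for these subjects largely from treated ones.

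Finally, whether the SAP author knowingly departed from this protocol text is uncertain. The SAP cites protocol sections 7.2.2, 13.1.2, 13.2.1 and 13.3.1 for content that this protocol has at 5.5.1, 12.1.2, 12.2.1 and 12.3.1, and it cannot be confirmed that this text is the V2.0 that the SAP names. The two documents still disagree as they stand.

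**Conclusion.** The point holds as an undeclared narrowing of the FAS. The SAP set is a treated-only population analysed as randomised, in effect a modified intention-to-treat set, where the protocol specifies all randomised subjects. The consequence is confined to the FAS sensitivity analysis of the primary endpoint and to the secondary and exploratory efficacy analyses.

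A reader should not conclude that the non-inferiority or superiority decision is affected. Both are taken on the PPS, which untreated subjects cannot enter under either definition, and the sample size of 128 evaluable subjects is unchanged.

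The size depends wholly on how many subjects were randomised and not treated. That may be none. The range of about 2 to 8 subjects at 1% to 5% of 170 is an assumption, and no bias in points can be derived from the documents. The reason to act is that the correction is cheap and removes a possible arm-dependent exclusion in an open-label trial.

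**What to change.** - **SAP 6.2:** restore the FAS to all randomised subjects, analysed in the arm to which they were randomised.
- **SAP 7.2:** state that the Day 0 pre-treatment image is the baseline for subjects who never receive a study dressing.
- **SAP 15.1.2 and 15.2.1:** confirm that their missing volume and area are handled by the multiple imputation already planned for the FAS.
- **SAP 15.2.2:** confirm that those with no later image are censored at Day 0 for time to wound bed preparation, as the existing rule provides.
- **SAP section 9:** report the number randomised but not treated, by arm.

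If a treated-only set is really intended, it should be named as modified intention-to-treat, with the change recorded and justified in SAP section 2 as protocol 6.6 requires.

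The cost is a few sentences of SAP text, with no change to data collection or sample size. The downside is that a few subjects may rest wholly on imputed outcomes, and standard imputation will not by itself bring out a worse result in them. Those censored at Day 0 add no event information. If the untreated count is zero, the results do not change at all.

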6.3. SAFETY SET (SS)

Including all subjects who have received either VAC VERAFL0 or control treatment. The data set is used to evaluate the safety of this trial. SS will be analyzed according to the actual treatment group.

7. General Considerations

7.1. REFERENCE START DATE AND STUDY DAY

Study Day will be calculated from the reference start date, and will be used to show start/ stop day of assessments and events.

Reference start date is defined as the day of the first application of study device with complete date, and will appear in every listing where an assessment date or event date appears.

- If the date of the event is on or after the reference date then: Study Day = (date of event – reference date) + 1.
- If the date of the event is prior to the reference date then: Study Day = (date of event – reference date).

In the situation where the event date is partial or missing, the date will appear partial or missing in the listings, and Study Day, and any corresponding durations will be presented based on the imputations specified in Appendix 1; Partial Date Conventions.

7.2. BASELINE

The baseline period will be defined as the period from informed consent to the first study device administration. Unless otherwise specified, baseline is defined as the last non-missing measurement taken prior to reference start date (first dressing application). In the case where the last non-missing measurement and the reference start date coincide, that measurement will be considered pre-baseline, but Adverse Events (AEs) and medications commencing on the reference start date will be considered post-baseline.

7.3. RETESTS, UNSCHEDULED VISITS AND EARLY TERMINATION DATA

In general, for by-visit summaries, data recorded at the nominal visit will be presented. Unscheduled measurements will not be included in by-visit summaries.

In the case of a retest (same visit number assigned), the last available measurement for that visit will be used for by-visit summaries.

Early termination data will be mapped to the next available visit number for by-visit summaries.

Listings will include scheduled, unscheduled, retest and early discontinuation data.

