### 5.3.2 Evaluation of Safety

#### (1) Incidence of AEs (unit: %)

**Define:** an AE is any untoward medical occurrence in the course of a trial, whether or not related to the investigational device.

**Evaluation:** type, incidence, seriousness and relatedness of AEs/Adverse device effects (ADEs), and laboratory abnormalities will be reported.

**Formula:** incidence of AEs/ADEs = sum of subject who occurred AEs/ADs ÷ sum of subjects for each group × 100%.

**Statistical method:** the difference between investigational group and control group will be assessed.

**Note:** especially focus on the systemic reactions and local skin/tissue irritation (such conditions as wound secretions and swelling, pain, and local skin color change, etc.)

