## **5.5 Study Procedure**

### **5.5.1 Schedule of Activities**

**Schedule of Activities**

Procedures	Screening Day -3~0	Randomization Day 0	Dressing Change Visit (s)	End of Treatment Visit 	Withdrawal or Discontinuation Visit 
Informed Consent	X				
Demographics a	X				
Medical History	X				
Surgical History	X				
Wound History b	X				
Vital Signs c	X				
Physical Exam	X	X	X	X	X
Blood Routine Examination d	X			X	X
Blood Coagulation Function e	X				
Serum Pregnancy Test f	X				
Evaluate inclusion/exclusion criteria	X	X			
Wound Clinical Assessments g		X	X	X	X
Wound Surgical Debridement		X 			
Digital/3D Wound Imaging h		X	X	X	X
Randomization		X			
NPWT		X	X		
Dressing Changes			X		
Concomitant Medications	X	X	X	X	X
AEs/SAEs Review and Evaluation	X	X	X	X	X
Device Deficiencies		X	X	X	X

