15.5. SUMMARIES FOR NPWT APPLICATION

The application time (minutes) for each dressing change, any leaks and treatment settings will be listed and summarized by treatment group.

16. Exploratory endpoints

An exploratory analysis will be conducted on the exploratory endpoints (volume, area and granulation tissue) using the FAS. Listings will be presented and sorted by treatment group, subject id.

Repeated measure analysis of variance using mixed model on mean change in exploratory endpoints(volume, area and granulation tissue) at each dressing change time point as dependent

Analysis Plan

Protocol No.: KCI.VERAFLO.2018.02

variables with center, treatment group and treatment-by-center interaction as fixed factors, wound size (wounds surface area, $<15\text{cm}^2$ (ref), $15\text{-}30\text{cm}^2$, and $>30\text{cm}^2$) as covariate, and time point as repeated factor will be performed using mixed model. The P-value of center, treatment group, treatment-by-center interaction, wound size and time point will be reported. LS Means and LS Mean difference and P-values for LS Mean difference will be reported out for each visit.

Above statistical analysis method will be conducted on wound area.

An example of SAS code is provided:

```
Proc mixed DATA=xxx covtest metood=ml;
Class id treat center woundtype timepoint;
Model volume(or area,or granulation tissue)=treat center treat*center woundtype timepoint
/htype=3 s noint;
Repeated timepoint/type=sample (covariance structure may be TOFL, AR(1) or UN. Likelihood
ratio testing (LRT) may be used to select best fitting model
Subject=id(treat);
Run;
```

17. Evaluation of Safety

All outputs for safety outcomes will be based on safety set, and presented by treatment groups.

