18.1.1. All Adverse Events

The following AE summaries will be described frequency and percentage by treatment group and overall in an overview summary table:

- AEs
- Severity of AE (mild, moderate, severe)
- Serious AEs
- deaths
- Adverse Device Effect
- Serious Adverse Device Effect
- AEs leading to study termination

If a subject experienced more than one adverse event, the AE with the worst severity will be used in the corresponding summaries.

In addition, all AEs will be listed and presented by System Organ Class (SOC) and Preferred Term (PT) and also broken down further by maximum severity of event. If a subject reports an AE more than once within that SOC/ PT, the AE with the worst severity will be used in the corresponding severity summaries.

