18.2. LABORATORY EVALUATIONS

Laboratory assessment presentations will use SI Units. Laboratory results collected by the CRF will be included in the reporting of this study for Blood Routine Examination, Blood Coagulation Function, and the test items include:

Blood Routine Examination

- Red Blood Cell Count (RBC count, $10^9/L$)
- Hemoglobin(g/L)
- White Blood Cell count (WBC count, $10^9/L$)
- Platelet($10^9/L$)

Actual outcomes from the CRF will be listed, the shift from baseline according to markedly abnormal criteria will be provided in order of visit.

Blood Coagulation Function

- Fibrinogen
- Prothrombin Time (PT)

- Activated Partial Thromboplastin Time (APTT)
- International Normalized Ratio (INR)

Actual outcomes from the CRF will be listed.

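### The by-arm blood-count shift table omits unscheduled values and values superseded by a retest; a worst post-baseline shift table should be added beside it (minor)

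*SAP*

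**What the plan says.** SAP 7.3 sets two rules for by-visit summaries. The first is "Unscheduled measurements will not be included in by-visit summaries". The second covers repeats under the same visit number: "In the case of a retest (same visit number assigned), the last available measurement for that visit will be used for by-visit summaries". The same section keeps every value in the data listings: "Listings will include scheduled, unscheduled, retest and early discontinuation data".

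SAP 18.2 plans one laboratory summary. For the blood routine examination (red cells, haemoglobin, white cells, platelets), "the shift from baseline according to markedly abnormal criteria will be provided in order of visit". Coagulation results are only listed. SAP section 17 fixes the layout of safety outputs: "All outputs for safety outcomes will be based on safety set, and presented by treatment groups".

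The Schedule of Activities in Protocol 5.5.1 places the blood routine examination at Screening, at End of Treatment and at the withdrawal or discontinuation visit. None is scheduled at the dressing change visits. Protocol 5.3.2 (1), repeated in SAP 17.1, makes laboratory results part of the safety evaluation: "and laboratory abnormalities will be reported".

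**The concern.** Each subject supplies one scheduled blood count after baseline, and study treatment can last up to 14 days. A count taken in between is unscheduled by definition, and SAP 7.3 keeps it out of the only by-arm laboratory table. At the End of Treatment or withdrawal visit, a repeat under the same visit number replaces the value it was meant to check.

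Extra bloods and repeats are often prompted by a clinical worry or a surprising result, so the values left out may well be the ones of most interest for safety. Protocol 12.1.5 lists bleeding and localized infection among the anticipated events, and haemoglobin and white cell count are the collected measurements that bear on them. Investigators know the assignment, so the decision to repeat a test could differ between arms, and the table could then differ for that reason alone.

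**Working it through.** The documents state no figure on this point, so there is none to reproduce. The check is a reading of the rules in sequence, followed by an illustration on assumed rates.

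**Reading**

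1. The SAP 18.2 shift output is organised by visit, so the SAP 7.3 rules for by-visit summaries apply to it. SAP 18.2 states no exception.
2. Neither SAP 17.1 nor SAP 18.2 plans a worst-value summary or a count of subjects with any markedly abnormal value after baseline.
3. Four cases follow:

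| Blood count | Enters the by-arm shift table? |
|---|---|
| Taken between baseline and End of Treatment or withdrawal, repeated or not | No; it is unscheduled |
| Abnormal at End of Treatment or withdrawal, repeated as normal under the same visit number | No; the repeat replaces it |
| Normal at that visit, repeated as abnormal under the same visit number | The abnormal repeat enters |
| Abnormal at that visit, repeated later as an unscheduled test | The original abnormal value enters; the repeat does not |

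4. The replacement route therefore affects one sample per subject. The unscheduled route covers the whole treatment period. A subject with a mid-treatment abnormality still shows as abnormal if the End of Treatment value is also markedly abnormal.

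**Illustration of the replacement route (all rates assumed)**

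Let N be subjects per arm, p the true proportion with a markedly abnormal count at the visit, r the share of those retested under the same visit number, and q the share of retests that are normal.

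- Subjects missing from the table = N × p × r × q.
- Displayed proportion = p × (1 − r × q).
- N = 85 is the maximum per arm in Protocol 6.1.1. The values p = 5–20%, r = 0.4–0.9 and q = 0.3–0.7 are assumptions.
- Low end: 85 × 0.05 × 0.4 × 0.3 = 0.5 subjects.
- Middle: 85 × 0.10 × 0.8 × 0.5 = 3.4 subjects; displayed proportion 10% × (1 − 0.40) = 6%.
- High end: 85 × 0.20 × 0.9 × 0.7 = 10.7 subjects.
- Unequal retesting with a true 10% in both arms and q = 0.5: r = 0.8 in one arm displays 6%, and r = 0.4 in the other displays 10% × (1 − 0.20) = 8%.

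The share of abnormal visit values lost, r × q, runs from 0.4 × 0.3 = 12% to 0.9 × 0.7 = 63%. A range this wide shows only that the effect could be trivial or noticeable. Mid-treatment values come on top and cannot be counted even roughly, because the documents say nothing about how often such bloods are drawn.

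**The case against.** A reader might infer that abnormal results vanish from the safety report. They do not. SAP 7.3 and section 18 keep all values in the listings. Protocol 12.1.3 treats an abnormal laboratory result as something that can be a clinical event, and SAP 18.1.1 tabulates adverse events by arm and by maximum severity. Bleeding and localized infection would be counted as adverse events in their own right. This stands and limits the point to one descriptive table. What remains is that a listing is not a by-arm result, and that recording an event depends on the judgement of an unblinded investigator.

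A reader might also infer that the last-value rule deletes abnormal values selectively. Its text has no direction: a normal value followed by an abnormal repeat enters as abnormal. One-sided loss is a plausible result of how repeats are ordered, but the documents do not establish it. Nor do they say when repeats are taken. The idea that a repeat reflects recovery after the dressing has been removed is only a possibility.

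The contrast with adverse events, where "the AE with the worst severity will be used in the corresponding severity summaries", is suggestive but weak. That rule chooses among events already recorded, not among repeat measurements of one analyte.

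Two further objections stand. SAP section 8 lets the output templates override the text, SAP 7.3 opens with a general qualifier, and the SAP text does not define the markedly abnormal criteria, so the final output could differ from the written rule. A worst-value rule also has faults of its own: more samples give more chances of an abnormal result, and it would count a faulty sample that the repeat was meant to correct. The fix has to deal with both.

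**Conclusion.** The gap is real and minor. As written, the only by-arm laboratory summary omits every blood count between baseline and the End of Treatment or withdrawal visit, and omits an abnormal count at that visit when a same-visit repeat is normal. The plan's commitment to report laboratory abnormalities is then met by arm only in part.

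The conclusion rests on SAP 7.3 governing the SAP 18.2 shift output, which the text supports but an unseen template could change. It does not rest on the illustrative rates. Neither the primary endpoint nor the adverse event incidence is derived from this table, and SAP 18.2 plans no test on laboratory shifts.

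**What to change.** Keep the by-visit shift table and the SAP 7.3 rules for it. Add to SAP 18.2 a second table by treatment group: shift from baseline to the worst value after first dressing application. This is equivalent to the number of subjects with any markedly abnormal value in that period. Specify that it:

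- includes End of Treatment, withdrawal, retest and unscheduled values;
- takes the low and high directions separately for parameters where both matter, such as white cells and platelets;
- excludes samples documented as invalid;
- shows the number of post-baseline samples per subject by arm.

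State the markedly abnormal criteria for each parameter in the SAP, or point to where they are defined, and align the output template.

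The cost is a few lines of SAP text and one derivation, because SAP 7.3 already has these values listed. The downside is that displayed abnormality rates will be higher, and by more than a little if many values are now superseded. They will also depend partly on how often each arm is sampled. The by-visit table, which does not depend on extra unscheduled bloods, and the sample counts let a reader judge that.
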